5.6.3 Participant Transfers

If a participant moves from the area, making continued follow up at their consenting centre inappropriate, every effort should be made for them to be followed-up at another participating trial centre. Written informed consent should be taken at the new centre and then a copy of the participant's CRFs should be provided to the new centre. Responsibility for the participant remains with the original consenting centre until the new consent process is complete.

5.6.4 Loss to Follow-up

Where participants are lost to follow-up every effort will be made to trace their whereabouts. In our experience men with IDD and harmful sexual behaviour are very rarely lost to follow-up since they are usually on the sex offender register.

5.6.5 Trial Closure

The end of the trial is defined as 9 months following the last follow-up visit of the last patient randomised, to allow for data entry and data cleaning activities to be completed.

5.7 Sample Size

In our previous single group study, of 109 participants, the magnitude of change following treatment in the primary outcome measure, the QACSO, was 22.5 (SD = 24), and the observed ICC was 0.15 (Murphy, Sinclair, Melvin & Langdon, 2023). Assuming a similar change in the intervention group in this new study and a change of no more than one fifth of this in the controls (it is unlikely to be greater given the lack of CBT intervention in this group directed at sexual behaviour), we would expect a mean difference of around 18 units in the QACSO between the two groups. This led to a proposed sample size of 164 in our first Stage 2 submission to NIHR. However, this was considered by the HTA panel to be relying on too large an expected effect size, i.e. one of 0.75 standard deviations, and consequently running the risk of an inflated Type II error. We have, therefore, revised our calculations considering smaller effect sizes. We now propose using 30 sites and a total target sample size of 240. Under the same assumptions (ICC = 0.15 and an attrition rate of 20%), this would provide statistical power of 90% for an effect size of 0.607 and 80% for an effect size of 0.525. These would translate into 14.5 and 12.6 units difference on the QASCO. In our experience in our previous studies, attrition is less than 20% and, we believe the risk of a Type II is now well mitigated against.

5.8.2 Retention

Men will be encouraged to stay in the trial, through to the end of the trial. They will receive a £10 voucher to reward them for their effort and time, at each assessment. They will also receive letters from the trial staff thanking them for their help at the four time points (see Table). In our experience men with IDD really appreciate such letters as correspondence, thanking them, is rare in their lives.

5.9 Assignment of Intervention

The trial is a cluster-randomised controlled trial.

5.9.1 Allocation

5.9.1.1 Sequence generation -

Participating sites will be randomly allocated to either the group CBT programme or treatment as usual with a 1:1 ratio of allocation. Allocation will occur after site eligibility has been established and in two tranches: the first 10 sites will comprise the pilot phase, the remaining 20 will be allocated after month 13. Sites will be randomly allocated instantaneously, 5 in each group for the pilot, and 10 to each group for the remaining trial period. Random allocation will be the responsibility of Norwich CTU. The staff responsible will be blinded to site identity.

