5.10.4 Statistical Methods

5.10.4.1 Outcomes

The primary outcome measure will be the Questionnaire on Attitudes Consistent with Sexual Offending (QACSO) score. Secondary outcome measures are the further occurrences of harmful sexual behaviour, sexual knowledge scores, victim empathy scores, locus of control and self-esteem scores.

The EQ-5D-5L will also be completed for health economics purposes. These measures at baselines, 8 months, 12 months and 24 months will be captured using the same instruments (see Table page 26).

The primary efficacy analysis will be of the QACSO at 12 months. A general linear model with baseline QACSO as a covariate will be used as the primary means of analysis. Allocated treatment group will be included as a fixed effect. Due to randomisation being at the site level, rather than the individual level, generalised estimating equations (GEEs) will be used for parameter estimation to adjust for correlations between participants within sites. All estimates will be provided with 95% confidence intervals. Additional prognostic variables will be included in the analytical model as specified prior to any analysis, in the statistical analysis plan. Statistical significance will be set at the two-sided 5% level. All secondary outcomes will be analysed in an analogous manner.

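### Sites are randomised in two separately balanced tranches, but the named primary-model terms do not include tranche; adding it costs almost nothing and protects precision if the tranches differ

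*Protocol*

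**What the plan says.** Protocol section 5.9.1.1 sets a 1:1 allocation of sites in two tranches: "the first 10 sites will comprise the pilot phase, the remaining 20 will be allocated after month 13". It fixes the split as 5 and 5 sites in the pilot and 10 and 10 afterwards. Section 4.3.1 keeps all pilot data in the later analyses, so both tranches enter the primary comparison.

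Section 5.10.4.1 gives the primary model for QACSO at 12 months: "A general linear model with baseline QACSO as a covariate will be used as the primary means of analysis", and "Allocated treatment group will be included as a fixed effect". GEE handles the correlation within sites. The same section says that additional prognostic variables will be specified in the SAP before any analysis, and that secondary outcomes will be analysed in the same way. Tranche is neither named nor ruled out.

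On size, section 5.7 says "We now propose using 30 sites and a total target sample size of 240". With an ICC of 0.15 and 20% attrition it claims that "this would provide statistical power of 90% for an effect size of 0.607 and 80% for an effect size of 0.525".

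**The concern.** When allocation is forced to balance within a factor, a difference in outcome between the levels of that factor cannot move the treatment contrast. If the factor is left out of the model, the difference still goes into the estimated variance between sites. The estimated standard error then exceeds the true one, the test becomes conservative and some power is lost. With 30 randomised units there is little precision to give away.

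There is also a practical reason to name the term. The amendment log (section 7, version 1.1) records that stratification by region was dropped. A team that regards its trial as unstratified may not notice that the two-step allocation still creates a stratum. What section 5.10.4.1 defers to the SAP is prognostic variables; a factor created by the allocation scheme might not be thought of under that label.

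**Working it through.** **Inputs.** From section 5.7: 30 sites, 240 men, ICC 0.15, attrition 20%, SD 24, effect sizes 0.525 and 0.607. From 5.10.4.1: two-sided 5%. From 5.9.1.1: 5:5, then 10:10. The gap between tranches after baseline adjustment is not in the Protocol. I assume 0.2, 0.3 and 0.5 SD (4.8, 7.2 and 12 QACSO units), with 0 and 0.75 SD as outer cases.

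**The plan's own power.** After attrition, 240 × 0.8 = 192 men, or 6.4 per site and 96 per arm. The design effect is 1 + 5.4 × 0.15 = 1.81 and the effective number per arm is 96/1.81 = 53.0. The normal formula gives 87.8% at 0.607 and 77.1% at 0.525, not 90% and 80%. The stated values appear if all 240 are analysed: design effect 1 + 7 × 0.15 = 2.05, 120/2.05 = 58.5, and a t test with 58 per arm gives 90.0% and 80.05%. That is a separate matter. I use 192 men and a site-level t reference below, so the starting power is about 74%.

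**Standard error with tranche in the model (SD units).** The variance of a site mean is 0.15 + 0.85/6.4 = 0.2828. With 15 sites per arm, SE = √(2 × 0.2828/15) = 0.194. This is also the true sampling SE without the term, because of the balance.

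**Standard error without tranche.** A gap g adds 15 × (1/3)(2/3) × g² = (10/3)g² to the residual sum of squares in each arm, so (20/3)g² in all. Spread over 28 degrees of freedom, this adds 0.238 g² to the estimated site-mean variance:

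SE = √(2 × (0.2828 + 0.238 g²)/15).

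**Power at 0.525 SD.** Approximately Φ((0.525 − t × SE)/0.194), with t = 2.048 on 28 df without tranche, and t = 2.052 on 27 df with SE 0.194 with tranche. With tranche this gives 74.3% at every gap (noncentral t: 74.1%).

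| Assumed gap (SD) | SE without tranche | Ratio to 0.194 | Power without tranche | Points lost |
|---|---|---|---|---|
| 0 | 0.194 | 1.00 | 74.4% | none |
| 0.2 | 0.197 | 1.02 | 73.3% | 1 |
| 0.3 | 0.201 | 1.04 | 71.9% | 2 |
| 0.5 | 0.214 | 1.10 | 67.4% | 7 |
| 0.75 | 0.236 | 1.21 | 58.6% | 16 |

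Simulation of site means (20,000 runs per gap) agrees. Power with tranche stays at about 74%. Without it, type I error is about 4.7%, 4.4%, 3.2% and 2.0% at gaps of 0.2, 0.3, 0.5 and 0.75 SD.

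**Dependence on the GEE standard error.** These figures use a model-based SE with a t reference. With an uncorrected sandwich SE and a z test on 30 sites, simulated type I error without tranche is about 7.0% at no gap, 6.0% at 0.3 SD and 4.6% at 0.5 SD. With tranche it is about 7.4%.

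**The case against.** The strongest reply is that the model is still open. Section 5.10.4.1 says that further variables will be specified in the SAP, and a full covariate list is commonly left there. This stands: a reader might infer that the Protocol excludes tranche, and it does not. What can be said is that the named terms omit a factor fixed by the Protocol's own allocation scheme, and that nothing commits the SAP to it.

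Second, the size rests on an assumed gap, and a material loss needs a large one. A gap of 0.5 SD is 12 QACSO units, close to the 12.6 units of the 0.525 SD effect, and it would have to remain after adjustment for baseline QACSO. This stands, and is why the point is modest.

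Third, a reader might take the amendment log as evidence that the tranches differ. In January and March 2023, after first enrolment in April 2022, four-man groups became possible, eligibility was widened and sex education was allowed in TAU. The Protocol gives no calendar date for month 13, so these changes are not shown to fall on the tranche boundary. The sex-education change also acts on one arm only, so it would mainly be an interaction, which a main effect for tranche does not model. The log makes a gap possible and does not establish one.

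Fourth, a reader might conclude that the planned interval is simply too wide. That holds only against the same method with tranche included. With an uncorrected sandwich and a small gap, the interval is too narrow in absolute terms, with or without tranche.

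Fifth, a reader might infer that power must fall below plan. That follows only if the ICC of 0.15 excludes the tranche gap, which section 5.7 does not say. If 0.15 already contains it, what is lost is a possible gain: about 76% without tranche against 82% with it, at a 0.5 SD gap.

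**Conclusion.** The point holds as a modest one about precision. Tranche is a balanced allocation factor that the named model terms omit. There is no bias in the treatment estimate. Relative to the same analysis with tranche, the standard error is about 2%, 4% and 10% larger at assumed gaps of 0.2, 0.3 and 0.5 SD, with about 1, 2 and 7 points of power lost at 0.525 SD, and no loss at zero gap. The figures assume 6.4 men analysed per site, an ICC of 0.15 within tranche and a site-level t reference. The Protocol supports neither a claim that tranche has been ruled out nor a claim that the tranches do differ. The case for acting is that the term has almost no cost and the gap cannot be known in advance.

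**What to change.** In section 5.10.4.1, name randomisation tranche (pilot 10 sites or remaining 20 sites) as a fixed effect in the primary GEE model and in the analogous secondary models, and carry the same term into the SAP before any analysis.

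The cost is one sentence and one of 28 site-level degrees of freedom; no new data are needed. At zero gap the effect on power is negligible (74.3% against 74.4%). The term does not cure the small-sample behaviour of sandwich standard errors with 30 sites, which has to be settled separately.

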5.9.1.2 Allocation concealment mechanism

As allocation will be instantaneous, a random sequence will be generated, using a small block length given the small sample size. The sequence will be generated by a member of the Norwich CTU data management staff.

5.9.1.3 Allocation Implementation

After the instantaneous randomisation, the allocation of each site will be communicated to the trial manager, who will communicate directly with the study sites. This allocation will not be communicated to research assistants or members of the CTU who are to remain blind to site allocations.

5.9.2 Blinding

All researchers collecting data will be blinded to treatment arm allocation. The Chief Investigator will not be blinded. The trial manager, the local site PIs and treating therapists cannot be blinded.

5.10 Data Collection, Management and Analysis

5.10.1 Data Collection Methods

Each participant will be given a unique trial Participant Identification Number (PID). Data will be collected at the time-points indicated in the Trial Schedule.

The preferred method of data collection is collection on paper Case Record Forms (CRFs) followed by entry of data onto the central database, stored on servers based at NCTU. Data would be collected and entered by members of the HaSB-IDD trial team working within each research site. Staff will receive training on data collection and use of the online system (see Section 5.2).

Data collection, data entry and queries raised by a member of the HaSB-IDD trial team will be conducted in line with the NCTU and trial specific Data Management Standard Operating Procedure.

Identification logs, screening logs and enrolment logs will be kept on a secure database at Tizard Centre. Minimal participant identifiable data will be stored on the database in the study for the

purposes of contacting participants. There will be a clear logical separation of participant identifiable data from the trial data.

All data will be handled in accordance with the Data Protection Act 2018 (please refer to separate Data Management Plan and Data Collection and processing SOP).

5.10.2 Data Management

Data will be entered under the participants PID number onto the central database stored on the servers based at NCTU. Access to the database will be via unique, individually assigned (i.e. not generic) usernames and passwords, and only accessible to members of the HASB-IDD trial team at University of Kent, University of Warwick and NCTU, and external regulators if requested. The servers are protected by firewalls and are patched and maintained according to best practice. The physical location of the servers is protected physically and environmentally in accordance with University of East Anglia's General Information Security Policy 3 (GISP3: Physical and environmental security).

The database and associated code will be developed by NCTU Data Management, in conjunction with the HASB-IDD trial team. The database software provides a number of features to help maintain data quality, including; maintaining an audit trail, allowing custom validations on all data, allowing users to raise data query requests, and search facilities to identify validation failure/ missing data.

After completion of the trial the database will be retained on the servers of NCTU for on-going analysis of secondary outcomes, and prepared for archiving in accordance with NCTU archiving guidance. The trial database will be archived according to Sponsor SOPs, or according to NCTU archiving guidance, where a Sponsor SOP doesn't exist.

The identification, screening and enrolment logs, linking participant identifiable data to the pseudoanonymised PID, will be held locally by the trial site and by the trial team at Tizard Centre. This will either be held in written form in a locked filing cabinet or electronically in password protected form on NHS/ Tizard secure service computers. After completion of the trial the identification, screening and enrolment logs will be stored securely by the sites and Tizard for 5 years unless otherwise advised by NCTU/ Tizard Centre.

5.10.3 Non-Adherence and Non-Retention

No participant will be excluded on the basis of non-adherence to therapy according to the treatment arm. Any participant withdrawing from therapy will remain within the trial, unless wishing to withdraw, and all efforts will be made to collect study data.

5.10.4 Statistical Methods

5.10.4.1 Outcomes

The primary outcome measure will be the Questionnaire on Attitudes Consistent with Sexual Offending (QACSO) score. Secondary outcome measures are the further occurrences of harmful sexual behaviour, sexual knowledge scores, victim empathy scores, locus of control and self-esteem scores.

The EQ-5D-5L will also be completed for health economics purposes. These measures at baselines, 8 months, 12 months and 24 months will be captured using the same instruments (see Table page 26).

The primary efficacy analysis will be of the QACSO at 12 months. A general linear model with baseline QACSO as a covariate will be used as the primary means of analysis. Allocated treatment group will be included as a fixed effect. Due to randomisation being at the site level, rather than the individual level, generalised estimating equations (GEEs) will be used for parameter estimation to adjust for correlations between participants within sites. All estimates will be provided with 95% confidence intervals. Additional prognostic variables will be included in the analytical model as specified prior to any analysis, in the statistical analysis plan. Statistical significance will be set at the two-sided 5% level. All secondary outcomes will be analysed in an analogous manner.

5.10.4.2 Statistical Analysis Plan

Following Norwich CTU guidelines, we will produce a detailed statistical plan (SAP) before the end of data collection and ask for approval from data oversight committees. The SAP will follow guidance provided by Gamble et al (2017).

5.10.4.3 Additional Analyses

Currently no additional analyses (either formal interim analyses or subgroup analyses) have been planned. Any additional formal analyses will need to be pre-specified in the statistical analysis plan prior to any formal analyses.

5.10.4.4 Analysis Population

The efficacy analysis will be on the Intention-to-Treat population, consisting of all individuals randomised to the study, analysed according to the arm to which they were allocated, irrespective of the treatment received

5.10.4.5 Missing Data

The primary analysis will consist of complete cases, i.e. those with complete data available for the analytic model. Where the number of participants with missing data excluding analysis is deemed non-trivial (more than 5% and less than 50%), a formal imputation approach will be used. This will involve multiple imputation using an imputation model that will include, as a minimum, the variables included in the analytical model.

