The participants recruited for the trial will not necessarily have been convicted or even charged for sexual crimes, given the arbitrariness of police involvement for those with IDD, but there will need to be very good evidence from carers and case notes of harmful sexual behaviour. HSB will be defined as sexual behaviour in which the other person was not consenting (or was unable to consent), and the sexual behaviour would be defined as illegal (whether or not the police had been involved). Most men presenting for treatment in clinical services for this kind of behaviour have a history of more than one incident. Incidents may not have been reported by the victim (who may be someone with more severe intellectual disabilities and may have very poor or no verbal communication skills). The incidents also may not have been reported to the police by professionals or someone in the community, because they realise the person has intellectual disabilities and they may think that they are not suitable to be dealt with by the Criminal Justice System.

*A few men with IDD and HSB decide that they wish to adopt the female gender. We will not exclude these transgender individuals from the trial. For ease, though, we have continued to refer to 'men' in this protocol. That should be taken as meaning 'assigned male at birth'.

It is anticipated that some men may be in low or medium secure health services, while some may be legally unrestricted, living in the community. Groups may include some or all of these categories (as was the case in SOTSEC-ID, 2010 and in Heaton and Murphy, 2013). It is likely that all participants will also have family carers or paid carers who will be invited to take part in the research (see below for details). Men in prisons, on probation (with a sex offender treatment order) and in high secure services will be excluded. If men are imprisoned during the treatment trial (i.e. during the six months of treatment) they will discontinue in the treatment group but be included in the intention to treat analysis.

Participants with autism will **not** be excluded as long as they also have mild or borderline ID. Though they may find group treatment difficult, the evidence is that many were included in previous group CBT research (e.g. SOTSEC-ID, 2010; Heaton & Murphy, 2013) and they themselves have said they found the treatment helpful (Melvin, Langdon & Murphy, 2019).

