5.6.2 Early Stopping of Follow-up

If a participant chooses to discontinue their trial treatment, they should continue to be followed up as closely as possible to the follow-up schedule defined in the protocol, providing they are willing. They should be encouraged and facilitated not to leave the whole trial, even though they no longer engage in the trial treatment. If, however, the participant exercises the view that they no longer wish to be followed up, this view must be respected and the participant withdrawn entirely from the trial. University of Kent and NCTU should be informed of the withdrawal in writing using the appropriate HASB-IDD trial documentation. Data already collected will be kept and included in analyses according to the intention-to-treat principle for all participants who stop follow up early.

Participants who stop trial follow-up early will not be replaced.

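### The complete-case primary analysis does not match the intention-to-treat population, drops men with an observed 8-month QACSO, and is not clearly ranked against the imputation that 20% attrition would trigger

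*Protocol*

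**What the plan says.** Four sections of the Protocol bear on who is in the primary analysis.

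- 5.10.4.4 Analysis Population: "The efficacy analysis will be on the Intention-to-Treat population, consisting of all individuals randomised to the study", by allocated arm and whatever treatment was received.
- 5.3.1 Eligibility Criteria, on men imprisoned during the six months of treatment: "they will discontinue in the treatment group but be included in the intention to treat analysis".
- 5.6.2 Early Stopping of Follow-up: "Data already collected will be kept and included in analyses according to the intention-to-treat principle for all participants who stop follow up early".
- 5.10.4.5 Missing Data: "The primary analysis will consist of complete cases, i.e. those with complete data available for the analytic model".

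Section 5.10.4.5 adds a conditional step. If the number with missing data is "deemed non-trivial (more than 5% and less than 50%), a formal imputation approach will be used", by multiple imputation with "an imputation model that will include, as a minimum, the variables included in the analytical model". It does not say whether that result replaces or supports the complete-case one, and it gives no rule for 50% or more.

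The analytic model (5.10.4.1) is a general linear model for the 12-month QACSO with baseline QACSO as covariate and arm as fixed effect. Further prognostic variables are left to the SAP. Site enters through GEE estimation. The QACSO is also collected at 8 months, as a secondary outcome (5.5.2.1). The sample size (5.7) allows for 20% attrition.

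**The concern.** The population section promises everyone randomised, while the missing-data section keeps only men with a 12-month score. A man seen at baseline and 8 months and then lost contributes nothing to the primary estimate, although his 8-month score is probably the best available guide to his missing value.

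The imprisoned man shows the conflict most clearly. Section 5.3.1 places him in the intention-to-treat analysis. Section 5.6.1 names team offices, the secure unit, the man's residence and, exceptionally, a web meeting as assessment settings. Prison is not among them, so he may well lack the primary outcome and be dropped.

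Section 5.4.6 lists imprisonment, deterioration in mental health and withdrawal of consent as reasons for stopping treatment. Only one arm is offered 100 hours of group CBT, so loss that differs by arm and relates to progress is plausible. At stake are the size of the headline effect and, if the two results differ, which one the trial reports as its answer.

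**Working it through.** **Inputs from the Protocol.** 240 men in 30 sites (8 per site), ICC 0.15, attrition 20%, SD 24 (all 5.7); two-sided 5% level (5.10.4.1). The smaller target effect reproduces: 0.525 × 24 = 12.6 QACSO points.

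**Does the trigger fire?** 5% of 240 = 12 and 50% of 240 = 120, so imputation applies with 13 to 119 men missing. Planned attrition is 0.20 × 240 = 48 men, well inside. At the planning assumption both a complete-case and an imputed result will exist.

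**What can the stated minimum add?** Suppose only the 12-month score is missing and values are imputed from arm and baseline, Y* = a + b·arm + c·baseline + noise, with a, b and c fitted in completers. Refitting the same model to observed and imputed values together returns b, up to simulation noise. The minimum therefore reproduces the complete-case estimate and any bias in it. The 8-month score is measured after randomisation, so it would not ordinarily be among the covariates of the analytic model.

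**When is the complete-case estimate biased?** Let e be the 12-month residual given arm and baseline. Then bias = E(e | observed, CBT) − E(e | observed, TAU). If loss is random, both terms are zero. If loss depends on the 8-month score equally in both arms, they cancel. Bias needs loss that differs by arm.

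**Size, first calculation.** Assumptions not in the Protocol: correlation with baseline 0.5, partial 8-to-12-month correlation 0.7, and loss in the CBT arm more likely at worse 8-month scores; 20% missing in each arm.

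| Odds ratio of loss per SD | Complete-case effect | Bias | Share of 12.6 |
|---|---|---|---|
| 1.5 | 13.55 | 0.95 | 8% |
| 2 | 14.26 | 1.66 | 13% |
| 3 | 14.99 | 2.39 | 19% |

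**Size, second calculation.** 1000 simulated trials per scenario, 30 sites of 8, ICC 0.15, true effect −12.6, about 20% missing and 10 imputations. Assumed correlations: baseline to 8 months 0.55, 8 to 12 months 0.75, baseline to 12 months 0.50. Analysis: linear model on arm and baseline with site-robust SE and t on 28 df (the Protocol names no working correlation). Cells give bias and 95% coverage.

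| Loss | Complete case | Minimum imputation | Plus 8-month score | Plus 8-month score and site (fixed effects) |
|---|---|---|---|---|
| Random | 0.18; 94.1% | 0.17; 92.3% | 0.13; 94.2% | 0.13; 96.3% |
| On 8-month score, equal by arm | −0.21; 94.3% | −0.18; 92.4% | −0.17; 93.4% | −0.17; 96.1% |
| On 8-month score, CBT arm only | −2.31; 91.2% | −2.29; 88.7% | −0.04; 94.1% | −0.05; 95.9% |
| On 8-month score, opposite by arm | −4.61; 79.5% | −4.61; 76.1% | 0.19; 94.3% | 0.13; 97.2% |

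Monte Carlo error of a bias is about 4/√1000 = 0.13, so the first two rows show no material bias. The last row is an extreme case and is not relied on. A third run, with correlations of 0.5 to 0.75 and an odds ratio of 2 per SD in the CBT arm only, gave about 1.2 points (1.2/12.6 = 10%) for both complete cases and minimum imputation, and near zero once the 8-month score was used.

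**Standard error when site is left out of the imputation.** In the second calculation under random loss, the model SE was 3.70 against an empirical 4.20 (ratio 0.88). Complete cases gave 3.99 against 4.17 (0.96). A separate run gave 0.156 against 0.171 (about 9% low), with type I error 7.2% against 5.1% for complete cases. In the third run the shortfall was only slightly larger than for complete cases. Site as fixed effects overshot: 4.18/4.13 = 1.01 to 4.26/3.97 = 1.07.

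**The case against.** A reader might infer that the planned imputation ignores site and the 8-month QACSO, that both results will therefore be wrong, and that the trial faces a type I error of 7.2%. The documents do not support this. Section 5.10.4.5 sets a floor and excludes neither variable. Section 5.10.4.2 promises a detailed SAP, which is not at hand, and auxiliary variables and clustering in an imputation model are ordinary SAP content. Because the analysis uses GEE by site, site can even be read as part of the analytic model. The 7.2% belongs to an imputation without site, which the Protocol does not prescribe; the stated primary analysis gave 5.1% under random loss.

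The intention-to-treat sections can also be read more narrowly. Section 5.10.4.4 mainly fixes analysis by allocated arm. Section 5.3.1 says that leaving treatment does not exclude an imprisoned man, and 5.4.6 keeps such men in follow-up where possible. Section 5.6.2 speaks of analyses in general, and the 8-month QACSO is analysed as a secondary outcome. The first sentence of 5.10.4.5 calls complete cases primary, so imputation reads naturally as supporting it, and 5.10.5.2 presents both for the economic analysis.

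Attrition may be lower than planned: 5.7 reports less than 20% in earlier studies and 5.6.4 says such men are very rarely lost. Men who leave during the six months of CBT may have no 8-month score to use. The simulated loss depends on the 8-month score, so including that score works by construction.

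Most of this stands and limits the point. It does not remove the literal mismatch between everyone randomised and complete cases, the discarding of observed 8-month scores from the primary estimate, or the lack of an explicit ranking.

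**Conclusion.** The point holds in a limited form. The complete-case primary analysis in 5.10.4.5 does not match the population in 5.10.4.4 or the wording in 5.3.1 and 5.6.2. At the planned attrition an imputed result will stand beside it without a clear rank. Imputing from the stated minimum alone would add no protection against bias.

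The size is conditional. With assumed correlations of 0.5 to 0.75, the effect is misstated by roughly 1 to 2.4 points on 12.6 (8% to 19%) if loss depends on the 8-month score in the CBT arm only. It is overstated if men doing worse leave. The upper end is about 0.6 of a standard error (2.4/4.0). If loss is random or depends on the score equally in both arms, the bias is about zero. Omitting site from the imputation can make the SE somewhat too small, by an amount that varied between runs. The Protocol gives no correlations and no missingness pattern, so these are ranges under stated assumptions and not a prediction that the result will be biased.

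**What to change.** Name one primary estimate of the 12-month QACSO contrast, valid under missing at random, that uses all observed QACSO scores and respects site. Either of these would do:

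- a longitudinal model of the 8- and 12-month QACSO with baseline as covariate, arm by time, and clustering by site and man, reporting the 12-month contrast; or
- multiple imputation by arm that includes the 8-month QACSO and site, followed by the planned GEE. A random site effect is preferable to fixed effects, which overshot the SE in the check above.

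Keep complete cases as a sensitivity analysis. Add a delta-adjusted analysis for data missing not at random, since neither option removes bias from loss that depends on the unseen score. State which result leads at every level of missingness, including 50% or more. Reword 5.3.1, 5.6.2, 5.10.4.4 and 5.10.4.5 so that they describe the same set of men.

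The cost is Protocol and SAP wording and modest programming. No new data are needed, because the 8-month QACSO is already scheduled. The limit is that men lost before 8 months are recovered hardly at all; for them the delta-adjusted analysis carries the weight.
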